CLINICAL EVALUATION OF HAIR REMOVAL AND PERMANENT HAIR REDUCTION
FOR SKIN TYPES V-VI USING INTENSE PULSED LIGHT

Clinical Study Protocol

CLINICAL INVESTIGATION PLAN (CIP)

March 3, 2015 Version 1.2

Protocol # CS0115

Study Sponsor: Venus Concept

Sponsor contact details:

Contact person: [name]

[contact] x 133

Email: [contact]

STATEMENT OF CONFIDENTIALITY

The information contained herein is Confidential Information that remains the sole and exclusive property of Sponsor and is expressly subject to the terms and conditions of the Clinical Trial Agreement signed by both the Investigator and Sponsor.

Study Personnel

Principal study Investigator		
Name:		
email:		
Tel:		
Fax:		
Additional contacts:		
Site name:	Principal Investigator	Sub Investigator
	Name:	Name:
	Email:	Email:
	Tel:	Tel:
	Fax:	Fax:
Site name:	Principal Investigator	Sub Investigator
	Name:	Name:
	Email:	Email:
	Tel:	Tel:
	Fax:	Fax:
Site name:	Principal Investigator	Sub Investigator
	Name:	Name:
	Email:	Email:
	Tel:	Tel:
	Fax:	Fax:
Site name:	Principal Investigator	Sub Investigator
	Name:	Name:
	Email:	Email:
	Tel:	Tel:
	Fax:	Fax:
Site name:	Principal Investigator	Sub Investigator
	Name:	Name:
	Email:	Email:
	Tel:	Tel:
	Fax:	Fax:

Study Synopsis

Study Title	Clinical evaluation of hair removal and permanent hair reduction for skin type V-VI using Intense pulse light.	
Protocol No:	CS0115	
Device Name:	Versa IPL device	
Design	Multi-center, blinded, baseline-controlled, prospective study	
Projected Study period	Initiation Date: January 2015	Completion Date: March 2016
Objectives	
Primary objectives
 
 • To evaluate the safety of hair removal using the Versa HR 690 nm applicator. • To verify the efficacy of hair removal and permanent hair reduction using the Versa HR 690 nm applicator. 
Secondary objectives
 
 • To evaluate subject's assessment of comfort associated with treatments. • To evaluate subject's satisfaction with hair removal treatments and assessment of improvement. 	
Hypothesis	The study will confirm that the Versa HR 690 nm applicator is safe for removal of unwanted hair, and will result in hair removal and permanent hair count reduction for patients with Fitzpatrick Skin Type V-VI.	
Study population	20 sites and One hundred and twenty (120) subjects, Fitzpatrick Skin Type V-VI. Up to 12 evaluable subjects will be enrolled per site.	
Main Inclusion Criteria	
 • Healthy adults, females or males older than 21 years of age with skin type V-VI; hair color Black or dark brown; having a suitable treatment area for hair removal. Two small anatomical areas (right and left axillae and double sided bikini line) or; • One double sided large area (right and left thighs)or; • One large area (whole back / abdomen) 
Other areas not defined above, as face, are not allowed to be treated.
	
Main Skin Related Exclusion Criteria	
 • Active infections in the treatment area. • Dysplastic nevi in the treatment area. • Tattoos in the treatment area. • Significant concurrent skin conditions or any inflammatory skin conditions in the treatment area. • Active cold sores, open lacerations or abrasions in the treatment area. • Chronic or cutaneous viral, fungal, or bacterial diseases. • Deep suntan, recent suntan, sunburn or artificially tanned skin. • Current skin cancer. • History of skin cancer or pre-cancerous lesions at the treatment areas. 	

Investigational Treatment and Study Duration	Each subject will receive six treatments at four to six weeks intervals and return for follow-up visits at one (\pm seven days), three (\pm seven days) and six (\pm seven days) months after the last treatment for evaluation of the treated areas.
Criteria for Evaluation	
Primary endpoints
 
 • Hair count reduction from photographs 3 months following the last treatment - FU2, as compared to baseline (hair removal) • Hair count reduction from photographs 6 months following the last treatment - FU3, as compared to baseline (permanent hair reduction) 
Secondary endpoints
 
 • Hair count reduction from photographs 1 month following the last Treatment - FU1 • Subject's assessment of comfort associated with treatments using a VAS scale, following each of the 6 treatments. • Subject's satisfaction with hair removal treatments and assessment of improvement using a five point scale, at visit 3, 6, 7, 8 & 9. • Immediate response following each treatment, defined as type and intensity of response and the time it takes for it to subside. Should be removed any adverse events associated with various setting used during the treatment and follow-up period.

Table of Contents

1	Introduction.....	8
1.1	Background.....	8
1.2	Rationale for Evaluation	8
2	Study Design.....	9
3	Study Objectives.....	9

1.2 Rationale for Evaluation

IPL technology works on the principle of selective absorption of energy by components of the hair follicle. The target chromophore is melanin in the hair bulb and outer root sheath zones of the hair follicle, while the competing chromophores are any other melanin-containing components of the skin and other light-absorbing components such as haemoglobin in blood vessels. Therefore, patients with darker skin types present a greater treatment challenge; the goal for these patients is to deliver the highest fluence to the hair follicles without causing injury to the epidermis. Many factors influence the efficacy of treatment such as spot size, divergence/convergence of the beam and wavelength that determines the depth of penetration, pulse duration, fluence and the adjacent cooling system⁷.

This clinical protocol is using a Versa IPL device with hair removal 690 nm wavelength applicator. The assumption is that the device physical characteristics of wave length, pulse duration and the rectangular type pulse together with an advanced cooling system will enable safe and effective hair removal and permanent hair reduction in subjects with dark skin type.

7. Liew SH (2002) Laser hair removal: guidelines for management. *Am J Clin Dermatol* 3:107-115

The objective of this clinical study is to evaluate the safety of hair removal and to verify the hair removal and permanent hair reduction for skin type V-VI using the Versa 690 nm applicator, as assessed by hair counts.

The use of the Versa has been determined to present non-significant risk in accordance with 21 CFR 812.3 for the intended use in this study, because the device is not:

- Intended as an implant and presents a potential for serious risk to the health, safety, or welfare of a subject;
- Is purported or represented to be for use supporting or sustaining human life and presents a potential for serious risk to the health, safety, or welfare of a subject;
- Is for a use of substantial importance in diagnosing, curing, mitigating, or treating disease, or otherwise preventing impairment of human health and presents a potential for serious risk to the health, safety, or welfare of a subject; or
- Otherwise presents a potential for serious risk to the health, safety, or welfare of a subject.

This study will be conducted in compliance with the protocol approved by the Institutional Review Board, and according to Good Clinical Practice standards. No deviation from the protocol will be implemented without the prior review and approval of the IRB except where it may be necessary to eliminate an immediate hazard to a research subject. In such case, the deviation will be reported to the IRB as soon as possible.

2 Study Design

This is a Multi-center, blinded, baseline-controlled, prospective study. One hundred and twenty (120) subjects that meet the inclusion criteria will be enrolled from the site's pool of patients, up to 12 subjects per site. Subjects should be of Fitzpatrick Skin Type V-VI, and have a suitable treatment area for hair removal.

Subjects will receive six treatments with the study device, at four to six week intervals upon re-growth of hair, followed by three and six month follow-up visits after the last treatment.

3 Study Objectives

3.1 Primary Objectives

- To evaluate the safety of hair removal using the Versa HR690 nm applicator.
- To verify hair removal and permanent hair reduction using the Versa HR 690 nm applicator, assessed by hair counts.

3.2 Secondary Objectives

- To evaluate subject's assessment of comfort associated with treatments.
- To evaluate subject's satisfaction with hair removal treatments and assessment of improvement.

4 Outcome Measures

4.1 Primary Effectiveness Endpoints

- Hair count reduction, as calculated from photographs and defined as (count-baseline)/baseline*100; 3 months following the last treatment FU2 (hair removal).

- Hair count reduction, as calculated from photographs and defined as (count-baseline)/baseline*100; 6 months following the last treatment FU 3 (permanent hair reduction).

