8.1 Study Hypothesis

The study will confirm that the Versa HR 690 nm applicator is safe for removal of unwanted hair, and will result in hair removal and permanent hair count reduction for patients with Fitzpatrick Skin Type V-VI.

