8.3 Study Analysis

The objective of this clinical study is to evaluate the safety of hair removal and to verify hair removal and permanent hair reduction using the Versa HR 690 nm applicator assessed by hair counts. For this purpose an average of hair count of 2 blinded reviewers will be done at baseline, following treatments, and at follow up visits. In case of a big discrepancy between 2 blinded reviewers, the hair count will be redone by a third blinded evaluator.

An intermediate safety report will be produced based on analysis of data collected post treatment number one of all the enrolled subjects. A Hair Removal report will be produced based on analysis of data collected at the three-month follow-up visit and a Permanent Hair Reduction report based on the analysis of data collected at the six-month follow-up visit will be the final report. The interim reports will not affect the continuation of the study. The study will regardless of the interim report results, be finalized according to this protocol.

The study reports will provide information for use in research & development, and future planned study. All statistical tests will be two-sided. The level of statistical significance for effectiveness analyses is five percent for all tests of differences. Paired t-test and/or Wilcoxon signed rank test will be used to compare the evaluations at the baseline and follow up sessions. Descriptive statistics and correlations between variables will be performed.

Safety: Adverse events reported will be listed, documenting course, outcome, severity, and possible relationship to the treatment.

9 Adverse Events

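### The permanence objective is tested only as FU3 against baseline, which shows that some reduction remains at 6 months but not whether the effect is holding or fading

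*Combined protocol and SAP*

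**What the plan says.** Section 3.1 makes permanence a primary objective: "To verify hair removal and permanent hair reduction using the Versa HR 690 nm applicator, assessed by hair counts". The hypothesis in section 8.1 is that the applicator "will result in hair removal and permanent hair count reduction".

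Section 4.1 gives two primary effectiveness endpoints with one formula, percent change in count from baseline. They differ only in the visit: "3 months following the last treatment FU2 (hair removal" for the first and "6 months following the last treatment FU 3 (permanent hair reduction" for the second. The synopsis names the comparator for the later one: "Hair count reduction from photographs 6 months following the last treatment - FU3, as compared to baseline (permanent hair reduction".

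The inferential method is in section 8.3: "Paired t-test and/or Wilcoxon signed rank test will be used to compare the evaluations at the baseline and follow up sessions". Also, "All statistical tests will be two-sided", and "The level of statistical significance for effectiveness analyses is five percent for all tests of differences". Section 8.3 and the notes to the Appendix I flow chart base the Permanent Hair Reduction report on the FU3 data.

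Section 7.2.1.2, Table 1 and Appendix I schedule blinded counts at baseline, FU1, FU2 and FU3. No section names a comparison of FU3 with FU2, a minimum reduction, a model of the course over follow-up, or a definition of permanent beyond the endpoint label.

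**The concern.** A test against baseline asks whether any reduction is left on one date. A reduction that is stable from 3 to 6 months passes it, and so does one that has lost half its size over the same period. Since the two primary endpoints share formula, test and comparator, the only thing that distinguishes permanence from hair removal is three more months on the calendar.

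The study is baseline-controlled with no concurrent control (section 2). The course of the counts over FU1 to FU3 is therefore its only internal evidence on durability, yet the plan gives that course no part in the permanence conclusion. At stake is the wording of the final report: it could confirm permanent reduction from a result that does not separate a lasting effect from a waning one.

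**Working it through.** **Inputs from the documents.** 120 subjects, 40 in each of three area groups (section 8.2); percent change from baseline (section 4.1); paired comparison, two-sided, 5% level (section 8.3). The sum 3 × 40 = 120 checks, but the sample size cannot be reproduced, because section 8.2 gives no effect size, standard deviation (SD) or power and describes the variance only as low.

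**Assumptions.** SD of percent change 20, 30 or 40 points; all 120 subjects have paired data; t-test on the percent-change scale. Section 4.1's formula makes a reduction negative; reductions are written here as positive numbers.

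**Step 1: smallest mean FU3 reduction that is significant.** Formula: t(0.975, n−1) × SD/√n. For n = 120 this is 1.980 × SD/10.954.

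| Assumed SD | n = 120 | n = 40 (one area group) |
|---|---|---|
| 20 | 3.6 | 6.4 |
| 30 | 5.4 | 9.6 |
| 40 | 7.2 | 12.8 |

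**Step 2: an effect that halves.** Suppose the mean reduction is 60% at FU2 and 30% at FU3. The FU3 test against baseline gives t = 30/(SD/10.954), which is 16.4, 11.0 and 8.2 at SD 20, 30 and 40. All are far beyond 1.980. In a simulation of 4,000 trials per scenario, with within-subject correlation 0.5 or 0.7, this profile passed in at least 99.6% of trials, including those with n = 40. A fall from 60% to 15% still passed in about 100%, 100% and 98% of trials at n = 120.

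**Step 3: what the paired FU3-minus-FU2 change would show.** SD of the difference = SD × √(2(1−ρ)), with the same SD at both visits. The 95% half-width at n = 120 is 1.980 × SD of the difference/10.954.

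| SD per visit | ρ | SD of difference | Half-width |
|---|---|---|---|
| 20 | 0.5 | 20.0 | 3.6 |
| 30 | 0.7 | 23.2 | 4.2 |
| 30 | 0.5 | 30.0 | 5.4 |
| 40 | 0.5 | 40.0 | 7.2 |

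A half-width of 3.6 with SD 30 per visit would need a correlation of about 0.78, since 2(1−ρ) = (20/30)² = 0.444. That is a favourable case, so 5.4 is the safer planning figure at SD 30. Even at 7.2, a 30-point loss would have an interval of about 22.8 to 37.2 points and could not be missed.

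**The case against.** The best defence is that the protocol uses permanent as a label for reduction from baseline at 6 months. On that reading the endpoint and the test match the label, and a reader who infers that the design fails its objective outright goes too far. This stands in part. The documents attach the word to the FU3 endpoint but never say that it means no more than reduction still present at that visit, and a reader of the final report will take more from it.

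A reader might also infer that the protocol itself expects the effect to fade, because treatments are given when hair has regrown. The documents do not support this. That wording (sections 2, 5.1 and 7.1) governs the four-to-six-week interval between treatments, and the area is shaved before each one (sections 7.4.1 and 7.4.2.2), so some regrowth follows from shaving alone. Nothing in the documents predicts the course after the sixth treatment. The fading profiles above are illustrations, not forecasts.

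Third, the loss would not be hidden. Percent reductions at FU1, FU2 and FU3 are all endpoints, and section 8.3 plans descriptive statistics, so a drop from 60% to 30% would appear in the study's own means. That is true. What is missing is the paired interval and any role for it in the conclusion.

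Finally, the FU3-minus-FU2 change cannot prove permanence either. Counts might rise early in that interval and then level off with a lasting reduction, and follow-up ends at FU3. It is therefore too strong to say that the word may be used only if the loss is shown to lie within a fixed margin. The documents give no basis for a margin, and meeting one would still say nothing beyond 6 months.

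**Conclusion.** The point holds as a gap in the analysis and in the wording of the conclusion, not in data collection. As planned, the FU3 test supports a statement that hair count is reduced 6 months after the last treatment. It carries no information on whether that reduction is holding.

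The thresholds in step 1 depend on the assumed SDs, and the 60%-to-30% profile is hypothetical. The conclusion does not depend on either: a comparison with baseline at one visit cannot measure change between two follow-up visits. The phrase in section 8.3 about baseline and follow-up sessions might loosely be stretched to cover comparisons between follow-ups, but none is named and the synopsis fixes baseline as the FU3 comparator.

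This is a cheap improvement that alters what the final report can conclude. A stable paired result would support durability to 6 months and no further.

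**What to change.** In sections 4.1 and 8.3, add to the Permanent Hair Reduction report the within-subject FU3-minus-FU2 change in percent reduction, from the averaged blinded counts, with its 95% confidence interval. Pool it over all subjects, because in a single group of 40 the half-width at a difference SD of 30 is about 9.6 points, against 5.4 for 120. Show the FU1 result alongside.

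State in advance that the durability statement rests on both this interval and the FU3-versus-baseline result. Where the interval shows material loss since FU2, word the conclusion as hair reduction at 6 months after the last treatment. Judge stability from the interval, not from a non-significant FU2-to-FU3 difference, which would not show it. In every case limit the claim to the 6 months observed. The sponsor may fix a margin for material loss beforehand, but the change does not require one.

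The cost is a few sentences of plan text and one paired estimate on counts already scheduled, with no new visits, subjects or procedures. The downside for the sponsor is a possibly less favourable claim.

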4.2 Secondary Endpoints

- Hair count reduction, as calculated from photographs and defined as (count-baseline)/baseline*100; 1 months following the last treatment FU1 (hair removal).
- Subject's assessment of comfort associated with treatments using a VAS scale.
- Subject's satisfaction with hair removal treatments and assessment of improvement using a five point scale.

4.3 Safety Endpoint

- Immediate response following treatment, defined as intensity of response and the time it takes for it to subside.
- Any adverse events associated with various setting used during the treatment and follow-up period.

5 Patient Population

5.1 Source and Sample Size

Subjects shall be recruited by the investigator from within the investigator's patient population. Subjects shall be with skin types V-VI and have visible hair at the designated treatment area.

Each site participating in this study will enroll up to 12 subjects according to the inclusion/exclusion criteria. Each subject (120 subjects) included for treatment will receive six treatments at four to six week intervals upon re-growth of hair and return for follow-up visits at one month FU1 (\pm seven days), three FU2 (\pm seven days) and six FU3 (\pm seven days) months after the last treatment for evaluation of the treated areas. Enrolled subjects that did not complete the full course of the study will be replaced.

5.2 Eligibility

Each subject will be evaluated by the Investigator to assess his/ her suitability for entry into this study according to the following criteria:

5.2.1 Inclusion Criteria

Subjects must meet all of the following inclusion criteria to be entered into the study:

1. Able to read, understand and provide written Informed Consent;
2. Subject has black or dark brown terminal hairs in the areas to be treated.
3. Terminal hair density requirement of greater than 15 hairs within the hair count site (3x3 cm area) as determined by manual hair count performed by the study investigator.
4. Healthy adult, male or female, 21 years of age or older with skin type V-VI;
5. Having a suitable treatment area for hair removal;
6. Able and willing to comply with the treatment/follow-up schedule and requirements;
7. Women of child-bearing potential (women who have not had a hysterectomy, bilateral oophorectomy or are not postmenopausal) are required to be using a reliable method of birth control at least three months prior to enrollment and throughout the course of the study.

5.2.2 Exclusion Criteria

Any of the following will exclude the subject from the study:

1. Subject has light, gray terminal or fine hairs in all/some parts of the treated area;
2. Pregnant, expectation of pregnancy, postpartum or nursing (<6 months);
3. Hormonal disorders that may affect hair growth;
4. Immunosuppressive diseases, including AIDS and HIV infection, or use of immunosuppressive medications;
5. Livedo reticularis;
6. Uncontrolled systemic diseases such as diabetes;
7. Active infections in the treated area;
8. Dysplastic nevi;
9. Significant concurrent skin conditions or any inflammatory skin conditions;
10. Active cold sores, open lacerations or abrasions;
11. Chronic or cutaneous viral, fungal, or bacterial diseases;
12. Current cancer;
13. History of skin cancer or pre-cancerous lesions at the treatment areas;
14. Use of Accutane™ (Isotretinoin) within the past six month;
15. Keloid or Hypertrophic scar formation in the treatment area;
16. Tattoos in the treatment area;
17. Bleeding coagulopathies or use of anticoagulants;
18. Auto-immune disorders;
19. Erythema abigne, when identified treatments should be discontinued;
20. Photosensitivity disorder that can be exacerbated by laser or intense light;
21. Herpes simplex in the treatment area;
22. Use of medications, herbal supplements, perfumes or cosmetics that may affect sensitivity to light;
23. Poor wound healing;
24. Sunburns;
25. Unable or unlikely to refrain from artificial tanning, including the use of tanning booths, prior (at least a month) and during the course of the evaluation;
26. Prior skin treatment with laser or other devices on the same treated areas within the last six months prior to study enrollment or during the course of the study.

6 Materials

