7.4 Pre-Treatment Procedures

7.4.1 Subject Skin care and medication

- Subjects will be instructed to avoid sun exposure for at least four weeks before treatment and to use broad spectrum sunscreen of no less than 30 SPF on a daily basis, replenishing it as often as needed throughout the course of the study. In addition Tanning is to be strictly avoided.
- Subjects should not pluck, tweeze, wax, use depilatory creams, electrolysis, hair bleaching agents, hair growth inhibitors (such as Vaniqa®) or any treatment with a laser or other devices in the study treatment throughout the course of this study and follow-up examinations.
- Immediately before treatment, the area will be shaved to the skin surface using foam or gel to minimize skin irritation.

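### The pre-baseline look-back covers only laser and other devices, so recent waxing, plucking or growth-inhibitor use can leave an unknown subset of subjects with an understated baseline count

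*Combined protocol and SAP*

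**What the plan says.** **Look-back.** Section 5.2.2, exclusion 26, rules out "Prior skin treatment with laser or other devices on the same treated areas within the last six months prior to study enrollment". No other criterion sets a period before entry for anything done to the hair in the treatment area.

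**Ban during the study.** Section 7.4.1 states: "Subjects should not pluck, tweeze, wax, use depilatory creams, electrolysis, hair bleaching agents, hair growth inhibitors", and adds laser or other device treatment. The period is "throughout the course of this study and follow-up examinations". Section 7.6.1 repeats the ban for tweezing, plucking, waxing, creams and other removal methods for the duration of the evaluation. It adds a seven-day interval before treatment and follow-up visits, for shaving only.

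**Entry requirements on hair.** Section 5.1 asks for visible hair in the designated area. Inclusion 3 (section 5.2.1) asks for more than 15 terminal hairs in the count site, by the investigator's manual count.

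**Timing.** Appendix I places the baseline photograph and counts at Visit 0, together with consent and eligibility. Section 7.3.1 allows treatment the same day or within a week. Its screening list has medical history and examination of the area, but no question about recent hair removal.

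**Use of baseline.** Section 2 describes a baseline-controlled study. Section 4.1 defines both primary endpoints, at three and six months, as change from baseline divided by baseline.

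**The concern.** The plan names a set of methods that must not be used while hair is being counted, yet lets the reference count follow directly after any of them except those that exclusion 26 covers. Every follow-up count is made after months under the ban; the baseline count need not be.

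With no untreated arm, any difference in conditions between baseline and follow-up is read as part of the device effect. If some hairs are missing or not visible at baseline and have returned by follow-up, the recorded reduction is too small in that subject. Because habits differ between people, the error also differs between people and adds to the spread seen by the paired tests in section 8.3. It may differ between body areas too, but that is an assumption.

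The damage could not be undone. Baseline cannot be retaken once treatment 1 has been given, and without a record of recent hair removal no sensitivity analysis could identify the affected subjects.

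**Working it through.** **Step 1. Does any rule reach back before baseline?** The protocol uses look-backs elsewhere: six months for isotretinoin (exclusion 14) and for laser or other devices (exclusion 26), at least a month for artificial tanning (exclusion 25), at least three months of birth control (inclusion 7), and at least four weeks for sun exposure (section 7.4.1). None covers plucking, tweezing, waxing, depilatory creams, bleaching or growth inhibitors. Electrolysis may fall under other devices. Even if the ban is taken to start at consent and the baseline photograph is deferred to treatment 1, it would cover at most seven days.

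**Step 2. How far does the 15-hair floor help?** Let B be the true count in the site and v the share visible at baseline. A subject qualifies if B × v is at least 16, so the largest hidden share is 1 − 16/B.

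| True count B (assumed) | Largest hidden share that still qualifies |
|---|---|
| 20 | 20% |
| 30 | 47% |
| 40 | 60% |
| 60 | 73% |
| 80 | 80% |

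The floor removes nearly cleared sites but leaves room for partly regrown ones. For B = 40, visible shares of 90%, 70% and 50% give 36, 28 and 20 hairs, all of which pass.

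**Step 3. Effect on one subject's endpoint.** Let R be the true reduction. Assume that the hidden hairs would be back by follow-up and respond to treatment like the rest. The follow-up count is B(1 − R) and the recorded baseline is Bv. By the formula in section 4.1, the recorded reduction is 1 − (1 − R)/v. B cancels.

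| True R (assumed) | v = 90% | v = 80% | v = 70% | v = 50% |
|---|---|---|---|---|
| 30% | 22.2% | 12.5% | 0% | increase of 40% |
| 50% | 44.4% | 37.5% | 28.6% | 0% |
| 70% | 66.7% | 62.5% | 57.1% | 40% |

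For example, with R = 50% and v = 70%: 1 − 0.5/0.7 = 28.6%.

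**Step 4. Effect on the study mean.** With a share p of subjects affected at v = 70% and R = 50%, the mean is (1 − p) × 50 + p × 28.6. The between-subject SD added by the mixture alone is (50 − 28.6) × √(p(1 − p)).

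| p (assumed) | Mean recorded reduction | Shift from 50% | Added SD |
|---|---|---|---|
| 10% | 47.9% | 2.1 points | 6.4 points |
| 25% | 44.6% | 5.4 points | 9.3 points |
| 50% | 39.3% | 10.7 points | 10.7 points |

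The documents give no value for B, R, v or p. Section 8.2 states no effect size, standard deviation or power, so there is no figure of the plan's own to reproduce.

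**The case against.** The strongest reply is that the entry criteria already deal with this. A reader might infer from exclusion 26 alone that anyone who waxed up to the day of baseline is eligible and enters with a false count. The documents do not support that: a site cleared just before the visit would fail both the visible-hair requirement and inclusion 3. This part of the reply stands, and the risk is confined to partly cleared or partly regrown sites with at least 16 hairs. It does not close the gap, as step 2 shows.

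The second reply is that the bias is conservative. That also stands. A reader who sees a biased baseline might infer inflated efficacy, but the error shrinks the recorded reduction and cannot by itself produce a false claim. It still matters, because the study sets out to verify the reduction by counts, and the added spread weakens the paired comparison.

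Third, the magnitudes are assumed. That is correct. At 10% of subjects affected the mean moves by only about 2 points, and the 0% reading needs half the hairs to be hidden. How long hair takes to return after each method is not in the documents either.

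Fourth, section 7.4.1 does not say why it bans these methods. A reader might infer that it does so to protect the count, but the protocol attaches count accuracy only to the no-shave interval in section 7.6.1. The argument here needs only the difference in conditions between baseline and follow-up.

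**Conclusion.** The gap is real: no rule keeps the methods listed in section 7.4.1, other than devices, away from the baseline count. The consequence is conditional. An unknown subset of subjects can enter with an understated baseline, which lowers the recorded reduction and adds variation.

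On the assumed figures, the study mean falls from 50% to between 47.9% and 39.3% as the affected share goes from 10% to 50%, with 70% of hairs visible in those subjects. This rests on the assumptions in step 3 and on regrowth being incomplete at Visit 0. The plan sets no minimum percentage reduction, so one cannot say whether such a shift would change a conclusion.

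Two extensions are tempting and are not made. Exclusion 3 covers "Hormonal disorders that may affect hair growth" but not medicines, and a reader might infer a parallel gap there. The documents identify no systemic medicine with such an effect and give no size. A reader might also infer that recently epilated follicles hold less pigment and respond less at treatment 1. Sections 1.1 and 1.2 name melanin as the target but say nothing about epilated follicles.

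The point should be corrected before enrolment; it does not undermine a positive result.

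**What to change.** Extend exclusion 26, or add a criterion, so that the methods listed in section 7.4.1 are also barred in the treatment area for a fixed period before the baseline photograph. The sponsor should set the period and justify it by the time hair needs to return after each method.

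Allow re-screening once the period has passed, with shaving permitted meanwhile. Make clear that the no-shave interval in section 7.6.1 also applies before the baseline photograph.

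Add a question to the screening list in section 7.3.1, and record the last hair-removal method and its date on the CRF at Visit 0. A sensitivity analysis by time since last removal then becomes possible.

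The cost is one amended criterion and one or two CRF fields. Some subjects will wait before baseline, so enrolment will be slightly slower.
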